10.6 Supportive Secondary Endpoints

N/A

10.7 Explorative /Tertiary Effectiveness Endpoint(s)

N/A

11 INTERIM ANALYSES

In addition to the final study report planned for December 2023, there will be two annual interim reports (one per year) on study progress and any emerging safety data. These are planned for December 2021 and December 2022. Both country-specific and pooled results (meta-analysis) will be presented in the final report, where data are available.

There will not be any adjustment for multiple comparisons doing several analyses, nor corrections where multiple comparisons are done.

12 RISK-BENEFIT ASSESSMENT

N/A

13 CHANGES FROM THE PROTOCOL

The statistical analysis are described in further details and explanatory figures have been added, compared with the outlines in the protocol.

The protocol states that 'Fatal and non-fatal MACE and VTE events will be assessed separately', but this is only possible in Denmark and Sweden. The SAP is updated.

The protocol stated that 'The length of the permissible gap will be varied (shortened or lengthened).', while the SAP specified 'The length of the permissible gap will be shortened'. Also the following has been added '. If two treatments with different ATC-codes are dispensed (or prescribed) on the same day only the treatment with the highest number of supplied days should be kept in the analysis.', since the previous formulation would give too long treatment periods.

Protocol stated in section 9.3.21 that 'If, recurrent events have been observed, a Cox model for recurrent events may be applied which will be detailed in the SAP.' The SAP specifies that this analysis will be presented if more than 5% of the patients has recurrent events.

Meta-analysis is in the protocol 'specified as random effect model', but the analysis has been expanded to both random and fixed effect model in the SAP and this is also reflected in the table shells.

Protocol stated that 'All adverse events/reactions collected for the study will be recorded and summarized in the interim *safety* analysis and in the final study report.' The SAP specifies that 'All adverse events/reactions collected for the study will be recorded and summarized in the interim analysis and in the final study report'. The word 'safety' was deleted since all statistical analysis will be presented in the yearly reports, except the meta-analysis.

The analysis of contraindications have been simplified and corrected compared with the protocol. Only one subpopulation for defining contraindications will be created, not the suggested 3 subpopulation, so that the extra medical conditions in secondary objective 5a, 5b, and 6 have been omitted, since it is not reasonable to have different contraindication at baseline for a possible future event. The usage of concomitant medical usage has also been omitted, since it is the condition at baseline that must determinate initiation of Nocdurna ® usage, not a future concomitant medical prescription, unknown to the prescribing physician at the index date.

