9.2.5 Subpopulations of interest

Elderly patients (≥65 years of age at index) will be considered a subpopulation of special interest, for which separate analyses will be performed.

Furthermore, the following patient groups will be considered as subpopulations of special interest, as they are contraindications for NOCDURNA use. Numbers permitting, sub-analyses will be performed according to the NOCDURNA and the LUTS group overall and by the elderly.

For the primary outcome:

- History of hyponatraemia
- Polydipsia
- Concomitant use of loop diuretics
- Concomitant use of glucocorticoids
- Congestive heart failure (chronic)
- Kidney disease (chronic kidney disease stage 3 and over)
- Syndrome of inappropriate antidiuretic hormone secretion (SIADH)

- Additionally, for the cardiovascular disease outcome: uncontrolled hypertension
- Additionally, for the thromboembolic event outcome: coagulation disorders

See Annex 3, Table A2 for diagnostic codes.

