9.7.2.9 Secondary objective 7: Comparative analyses

Where possible, for the comparative analyses of primary and secondary outcomes of interest, the same analyses (Poisson regression) as in Section 9.7.2.1 will be applied but now with treatment group (NOCDURNA/LUTS) as an additional factor. To investigate if the incidence rate ratio (IRR) for the Poisson regression of NOCDURNA to LUTS depend on confounders, treatment by confounder interaction terms will be investigated to see if and to what extent (quantitative or qualitative) the IRR depend on the respective confounding factor. These multiple regression methods will be detailed in the SAP.

9.7.2.10 Secondary objective 8: Cardiovascular and thromboembolic events of interest resulting in treatment withdrawal

The analysis of this outcome will be performed analogous to that of incident events of symptomatic hyponatraemia (see 9.7.2.1) for NOCDURNA only. MACE and VTE events considered to be associated with treatment cessation will be those events for which the event date occurs within 14 days prior to the treatment cessation date (see section 9.3.1). Serious MACE and VTE events will be defined as a primary or secondary diagnosis of MACE or VTE recorded in a hospital intensive care unit. This can be only evaluated in Sweden.

9.7.2.11 Secondary objective 9: Incidence rate in patients stratified according to the label by proxy

The analysis of this outcome will be performed analogous to that of incident events of symptomatic hyponatraemia (see 9.7.2.1) for NOCDURNA only. The subgroup of patients adhering to the label will be defined by a proxy based on diagnosis and contra-indications as available in the respective registries. This will be detailed in the statistical analysis plan

In this analysis the outcomes specified as the primary objective and secondary objectives 1-6 will be repeated for the NOCDURNA only patients. The subgroup of patients adhering to the label will be defined by a proxy based on diagnosis and contra-indications as available in the respective registries based on the information in the SmPC. Two population will be created for all NOCDURNA patients, one with contra-indication for treatment and another as the remaining NOCDURNA patients without contra-indication. The contra-indication for treatment must be present before the first recorded dispensation of NOCDURNA. This approach will be detailed in the statistical analysis plan

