Annex 3 Definitions of the LUTS cohort, outcome events and covariates

Table A1. ATC codes used to define the LUTS cohort

Characteristic	ATC code	Description
Overactive bladder	G04BD	Drugs for urinary frequency and incontinence
Benign prostatic hyperplasia	G04C	Drugs used in benign prostatic hypertrophy

Characteristic	ICD-10	ATC	Description
	code	code	
Hyponatraemia	E87.1		
Polydipsia	R63.1		
Loop diuretics		C03C	
Glucocorticosteroids		H02AB	
Congestive heart failure	150.2		Systolic (congestive) heart failure
	150.3		Diastolic (congestive) heart failure
	150.4		Combined systolic (congestive) and diastolic (congestive) heart failure
Chronic kidney disease	N18.3		Chronic kidney disease, stage 3 (moderate)
	N18.4		Chronic kidney disease, stage 4 (severe)
	N18.5		Chronic kidney disease, stage 5
	N18.6		End stage renal disease
Syndrome of inappropriate antidiuretic hormone secretion	E22.2		
Uncontrolled hypertension	I16		Hypertensive crisis
	167.9		Hypertensive encelopathy
Coagulation disorders	D68.0		Von Willebrand's disease
	D68.5		Primary thrombophilia
	D68.6		Other thrombophilia

Table A2. Codes used to define subpopulations of interest

Outcome	ICD-10 code	Description
Hyponatremia		
Hyponatraemia	E87.1	
Hyponatremia (biochemical definition)	n/a	Will be ascertained using biochemical definition: serum sodium concentration <135 mmol/L (mild hyponatraemia) Evaluated only in Denmark
Major cardiovascular events (MACE)	
Myocardial infarction	121, 122	
Stroke, ischemic	163.3-163.9, 166	
Major venous thromboembolic	c events	
Pulmonary embolism	126	
Deep vein thrombosis	180.1–180.9	
Portal vein thrombosis	181	
Mortality		
All-cause mortality	Any	Death from any cause
Heart failure		
Heart failure	150	

Table A3. Codes used to define outcome events

Table A4. Codes used to define covariates

Covariate	ICD-10 code	ATC code	Description/comment
Comorbidities			
History of hyponatraemia, MACE	Please refer to		
and VTE	Table A1		
Polyuria	R35		Polyuria
Diabetes mellitus	E10		Type 1 diabetes mellitus
	E11		Type 2 diabetes mellitus
	E12		Malnutrition-related diabetes
			mellitus
	E13		Other specified diabetes mellitus
	E14		Unspecified diabetes mellitus
Diabetes insipidus	E23.2		
Overactive bladder	N31.0		Uninhibited neuropathic bladder, not elsewhere classified
	N31.2		Flaccid neuropathic bladder, not elsewhere classified
	N31.9		Neuromuscular dysfunction of bladder, unspecified
	N39.4		Other specified urinary incontinence

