Table 41. Secondary objective 9. Incidence of all-cause mortality for patients with and without contraindications for Nocdurna ® use. Only Nocdurna ® patients

Repeat Table 38 with all-cause mortality as outcome for patients with and without contraindications for Nocdurna ® use. Only Nocdurna ® patients.

Table 42. Secondary objective 9. Incidence of major cardiovascular events for patients with and without contraindications for Nocdurna ® use. Only Nocdurna ® patients.

Repeat Table 38 with major cardiovascular events as outcome for patients with and without contraindications for Nocdurna ® use. Only Nocdurna ® patients.

Table 43. Secondary objective 9. Incidence of major venous thromboembolic events for patients with and without contraindications for Nocdurna ® use. Only Nocdurna ® patients.

Repeat Table 38 with major venous thromboembolic events as outcome for patients with and without contraindications for Nocdurna ® use. Only Nocdurna ® patients.

Table 44. Secondary objective 9. Incidence of acute exacerbation of congestive heart failure for patients with and without contraindications for Nocdurna ® use. Only Nocdurna ® patients.

Repeat Table 38 with acute exacerbation of congestive heart failure events as outcome for patients with and without contraindications for Nocdurna ® use. Only Nocdurna ® patients.

Sensitivity analysis, demographics are not repeated

Table 45. Sensitivity analysis. Incidence of symptomatic hyponatraemia in *country* with second prescription shifted to the end of the first.

Repeat Table 9 with incidence of symptomatic hyponatraemia in *country* with second prescription shifted to the end of the first as outcome.

Table 46. Sensitivity analysis. Incidence of hyponatraemia requiring hospital intensive care in *Sweden* with second prescription shifted to the end of the first.

Repeat Table 9 with Incidence of hyponatraemia requiring hospital intensive care in *Sweden* with second prescription shifted to the end of the first as outcome.

Table 47. Sensitivity analysis. Incidence of clinically significant hyponatraemia in *Denmark* with second prescription shifted to the end of the first.

Repeat Table 9 with incidence of clinically significant hyponatraemia in *country* with second prescription shifted to the end of the first as outcome.

Table 48. Sensitivity analysis. All-cause mortality in *country* with second prescription shifted to the end of the first.

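### The SAP drops uncontrolled hypertension and coagulation disorders from the contraindications for a reason that supports only a common list, so some patients the protocol calls contraindicated count as without contraindications under objective 9

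*Protocol*

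**What the plan says.** Protocol 9.2.5 introduces its subpopulations, other than the elderly, as groups of special interest "as they are contraindications for NOCDURNA use". After the conditions for the primary outcome it lists two more: "Additionally, for the cardiovascular disease outcome: uncontrolled hypertension" and "Additionally, for the thromboembolic event outcome: coagulation disorders". Sub-analyses are planned, numbers permitting, in both the NOCDURNA and LUTS cohorts. Annex 3, Table A2 gives the codes. Uncontrolled hypertension has I16 ("Hypertensive crisis") and I67.9. Coagulation disorders have D68.0 ("Von Willebrand's disease"), D68.5 and D68.6 (primary and other thrombophilia).

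For the label-adherence analysis, protocol 9.7.2.11 splits NOCDURNA patients into those with and those without a contraindication, with the proxy defined "as available in the respective registries based on the information in the SmPC". It leaves the detail to the SAP.

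SAP section 13 reports that one contraindication subpopulation will be used instead of three, "so that the extra medical conditions in secondary objective 5a, 5b, and 6 have been omitted". Its reason is that baseline contraindications should not differ according to a possible future event. The SAP text on secondary objective 9, which follows 10.2.9, then lists five diseases: history of hyponatraemia, polydipsia, chronic congestive heart failure, chronic kidney disease stage 3 and over, and SIADH. All remaining NOCDURNA patients form the group without contraindication. The split is applied to the primary objective and to secondary objectives 2, 3, 4, 5a, 5b and 6. One of the resulting shells is Table 43, "Incidence of major venous thromboembolic events for patients with and without contraindications".

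**The concern.** The reason given and the action taken do not match. An objection to lists that vary by outcome is fully met by one baseline list that contains both conditions and is used for every outcome. The SAP removes them for every outcome instead. It does not say that they are not contraindications, that the SmPC omits them, or that the registries cannot identify them.

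Objective 9 exists to show event rates when NOCDURNA is used according to its label, and thromboembolic events are a safety concern named in protocol section 7. Under the SAP rule, a patient whose only listed condition is thrombophilia enters the VTE table as a label-adherent user. A patient whose only listed condition is a hypertensive crisis enters the MACE table the same way. The reader of Tables 42 and 43 could not see this.

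**Working it through.** The documents give no figure to reproduce. The check is a comparison of lists, followed by an illustration on assumed inputs.

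**Step 1: the lists.**

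| Condition | Protocol 9.2.5 / Table A2 | SAP objective 9 / Table 71 |
|---|---|---|
| Hyponatraemia history, polydipsia, chronic heart failure, CKD stage 3 and over, SIADH | Listed | Listed |
| Uncontrolled hypertension | Listed: I16, I67.9 | Absent |
| Coagulation disorders | Listed: D68.0, D68.5, D68.6 | Absent |
| Loop diuretics, glucocorticoids | Listed | Absent, with a separate reason in SAP 13 |

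SAP 13 does not name the two conditions; this comparison identifies them. SAP 13 also mentions objective 6, but protocol 9.2.5 names no extra condition for it, unless heart failure exacerbation is read as part of the cardiovascular outcome. The deletion is not confined to the change summary, because the operative list and Table 71 both carry it.

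**Step 2: where the patients go.** Anyone with none of the five retained diseases is placed in the group without contraindications. Patients who have a dropped condition and also a retained one stay in the group with contraindications. The consequence therefore applies only to isolated cases.

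**Step 3: whether another output recovers them.** Baseline Table 10 and covariate Table 73 include I10 hypertension but no I16, I67.9 or D68 code. No shell stratifies MACE or VTE by either condition. Objective 9 is restricted to NOCDURNA patients, so the LUTS side of protocol 9.2.5 has no shell either.

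**Step 4: possible effect on a rate.** Let r be the event rate among patients in the without group who have neither dropped condition. Let p be the share of that group's person-time from patients with one, and RR their rate relative to r. The reported rate is (1-p)r + p·RR·r = r[1 + p(RR-1)].

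The documents give neither input. On assumed values:

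- p = 1%, RR = 2: factor 1.01
- p = 1%, RR = 3: factor 1.02
- p = 5%, RR = 4: factor 1.15
- p = 3%, RR = 10: factor 1.27

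The factor exceeds 1 only if RR exceeds 1.

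**Step 5: possible effect on the with/without ratio.** Assume the with group holds 20% of person-time at rate 3, and the without group holds 80%, of which 3% has RR = 2 against a rate of 1.

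- Under the SAP split: without rate = 0.97 + 0.03 × 2 = 1.03; ratio = 3/1.03 = 2.91.
- After moving those patients: with group person-time = 0.20 + 0.80 × 0.03 = 0.224; events = 0.20 × 3 + 0.024 × 2 = 0.648; rate = 0.648/0.224 = 2.89; without rate = 1; ratio = 2.89.

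Here the ratio falls slightly when the patients are moved, so the direction is not fixed.

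**The case against.** The change is disclosed and was delegated. Protocol 9.7 allows the SAP to revise the analyses, protocol 9.7.2.11 leaves the label proxy to it, and SAP 13 describes the change as a simplification and correction. All of that stands: departing from the protocol is not in itself an error. What it does not supply is a reason for deletion rather than a common list.

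Both documents tie the proxy to the SmPC, which is not at hand. If the SmPC does not list these conditions, the SAP grouping is right and nothing is inflated. This also stands, and it limits the point to a conditional one. The protocol does call the conditions contraindications, however, and the SAP gives no SmPC-based reason for disagreeing.

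The subgroups would be small. SAP Amendment 1 reports 1606 Swedish and 741 Danish NOCDURNA patients at the first interim report. An assumed 1-3% of these is about 16-48 and 7-22 patients, too few for precise VTE rates. Protocol 9.2.5 made the sub-analyses conditional on numbers for that reason.

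A reader might infer that the label-use MACE and VTE rates are overstated as a matter of fact, and that the contrast with contraindicated use is diluted. The documents support neither. The first needs the conditions to be contraindications and RR to exceed 1, which may not hold for D68.0. The second fails in Step 5.

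**Conclusion.** The point holds for the objective 9 split. As written, the SAP counts NOCDURNA patients whose only listed condition is uncontrolled hypertension or a coagulation disorder as without contraindications in Tables 11 and 38-44, although protocol 9.2.5 calls both conditions contraindications. The stated reason does not justify that, and the planned MACE and VTE sub-analyses are lost without any count of the patients concerned.

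The main cohort rates (such as Tables 19 and 23) and the incidence rate ratios against LUTS are not affected. The size of any distortion in the label-use rates is unknown. The factors of 1.01 to 1.27 in Step 4 only show its scale under assumed p and RR, and depend on the conditions being contraindications that raise risk. The direction of any change in the with/without ratio is not established.

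**What to change.** Reconcile protocol 9.2.5 with the SAP objective 9 list, SAP section 13 and Table 71, against the SmPC.

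- **If the two conditions stand as contraindications:** add them to the single baseline list in Table 71 for all outcomes, which respects the SAP's own argument. Check the Table A2 codes before use. Annex 3 is not consistent with itself elsewhere: polydipsia is R63.1 in Table A2 and R36.1 in Table A4.
- **If they do not:** say so in SAP 13 with the reason. Still report, numbers permitting, MACE by uncontrolled hypertension and VTE by coagulation disorder as protocol 9.2.5 plans, with D68.0 shown separately from D68.5 and D68.6.

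In either case, rows in Table 10 counting these patients would show how many are involved.

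The cost is a few code rows, or two extra runs of the existing macro for the NOCDURNA cohort in each country, repeated for LUTS if the protocol plan is kept in full. This assumes that the data extracts hold the codes, which the documents do not confirm. The drawback is small subgroups with wide intervals.

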between the countries for incidence rate ratio of symptomatic hyponatraemia	
Figure 22. Meta-analysis. A funnel plot to the left and a sensitivity plot to the right for incidence rate ratio of symptomatic hyponatraemia.	
Figure 23. Meta-analysis. A Galbraith to the left and a forest plot to the right illustrating the difference between the countries for all-cause mortality.	
Figure 24. Meta-analysis. A funnel plot to the left and a sensitivity plot to the right for incidence rate ratio of all-cause mortality	78
Figure 25. Meta-analysis. A Galbraith to the left and a forest plot to the right illustrating the difference between the countries for major cardiovascular events.	
Figure 26. Meta-analysis. A funnel plot to the left and a sensitivity plot to the right for incidence rate ratio major cardiovascular events.	78

Figure 27. Meta-analysis. A Galbraith to the left and a forest plot to the right illustrating the difference between the countries for venous thromboembolic events	78
Figure 28. Meta-analysis. A funnel plot to the left and a sensitivity plot to the right for incidence rate	70
ratio of venous thromboembolic events	78
Figure 29. Meta-analysis. A Galbraith to the left and a forest plot to the right illustrating the difference between the countries for congestive heart failure.	78
Figure 30. Meta-analysis. A funnel plot to the left and a sensitivity plot to the right for incidence rate ratio of congestive heart failure.	
Figure 31. Optional. Survival curve, if there are more than 5% of the patients that are having more	
than 1 event	79
Figure 32. Data flow in the SAS macros for Poisson regression.	82

An overview of the different tables divided by country of origin and objective is given below.

Observe that Table 1 to Table 7 are used in the ordinary text in this Statistical Analysis Plan.

Table 6. Overview of the different tables by country and objective.

Objective	Denmark	Germany	Sweden
Primary obj.	Table 9	Table 9	Table 9
Sec obj. 1, descriptive	Table 8, Table 10,	Table 8, Table 10,	Table 8, Table 10,
	Table 11, Table 12	Table 11	Table 11
Sec obj. 2, ICU	N/A	N/A	Table 13
Sec obj. 3; lab Na	Table 14, Table 15, Table 16, Table 17	N/A	N/A
Sec obj. 4, mortality	Table 18	Table 18	Table 18
Sec obj. 5a, MACE	Table 19, Table 20, Table 22	Table 19	Table 19, Table 20, Table 21,
Sec obj. 5b, VTE	Table 23, Table 24, Table 26	Table 23	Table 23, Table 24, Table 25
Sec obj. 6, CHF	Table 27	Table 27	Table 27
Sec obj. 7, comparative	Table 29, Table 30, Table 31, Table 32, Table 33, Table 34, Table 35, Table 36	Table 29, Table 30, Table 31, Table 32, Table 33, Table 34, Table 35, Table 36	Table 29, Table 30, Table 31, Table 32, Table 33, Table 34, Table 35, Table 36
Sec obj. 8, treatment withdrawal	N/A	N/A	Table 37
Sec obj. 9, contraindications	Table 38, Table 40, Table 41, Table 42, Table 43, Table 44	Table 38, Table 41, Table 42, Table 43, Table 44	Table 38, Table 39, Table 41, Table 42, Table 43, Table 44
Sensitivity, reduced gap	Table 45, Table 47, Table 48, Table 49, Table 50 Table 51	Table 45, Table 48, Table 49, Table 50 Table 51	Table 45, Table 46, Table 48, Table 49, Table 50 Table 51

Desmopressin One oral lyophilisate per day Statistical Analysis Plan	Trial Cod	e: 000248	18 August 2021 E-Statistical Analysis Plan-25098 (1.0) Page 47 of 91
Sensitivity, using prescribed dose	Table 52, Table 54, Table 55, Table 56, Table 57, Table 58	N/A	Table 52, Table 53, Table 55, Table 56, Table 57, Table 58
Meta-analysis			Table 59, Table 60, Table 61, Table 62, Table 63, Table 64, Table 65
Optional, Table 66			

Observe that Table 67 to Table 73 are to be used for giving instructions for the SAS programming.

An overview of the different figures divided by country of origin is given below. Figure 1 to Figure 3 is used in the text.

Objective	Denmark	Germany	Sweden
Primary obj.			
	Figure 6	Figure 6	Figure 6
Sec obj. 1, descriptive, age and exposure time	Figure 7, Figure 8, Figure 9, Figure 10, Figure 11, Figure 12, Figure 13, Figure 14	Figure 7, Figure 8, Figure 9, Figure 10, Figure 11, Figure 12, Figure 13, Figure 14	Figure 7, Figure 8, Figure 9, Figure 10, Figure 11, Figure 12, Figure 13, Figure 14
Sec obj. 2, ICU	N/A	N/A	Figure 15
Sec obj. 3; lab Na	Figure 16	N/A	N/A
Sec obj. 4, mortality	Figure 17	Figure 17	Figure 17
Sec obj. 5a, MACE	Figure 18	Figure 18	Figure 18
Sec obj. 5b, VTE	Figure 19	Figure 19	Figure 19
Sec obj. 6, CHF	Figure 20	Figure 20	Figure 20
Sec obj. 7, comparative	N/A	N/A	N/A
Sec obj. 8, treatment withdrawal	N/A	N/A	N/A

Table 7. Overview of the different figures by country and objective.

Desmopressin One oral lyophilisate per day Statistical Analysis Plan		Trial Code: 000248	18 August 2021 E-Statistical Analysis Plan-25098 (1.0) Page 48 of 91
Sec obj. 9, contraindications	N/A	N/A	N/A
Sensitivity, reduced gap	N/A	N/A	N/A
Sensitivity, using prescribed dose	N/A	N/A	N/A
Meta-analysis			Figure 21 to Figure 30
Optional, Figure 31			

Footnote: The following figures are an option for BIPS Figure 7, Figure 8, Figure 9, Figure 10, Figure 11, Figure 12, Figure 13, Figure 14

The following are the table shells.

Table 8. Patient disposition with number of patients in *country*.

	All Nocdurna ® patients	Nocdurna ®, Male	Nocdurna ®, Female	All LUTS patients	LUTS, Male	LUTS, Female
Number of extracted patients	Xx	Xx	Xx	Xx	Xx	Xx
Number of patients above 18 yy	Xx	Xx	Xx	Xx	Xx	Xx
Number of patients with 1 drug dispensation*)	Xx	Xx	Xx	XX	XX	XX
Excluded, age/gender is missing						
Excluded, vasopressin treated	Xx	Xx	Xx	Xx	Xx	Xx
Excluded, <12 month records before index date	Xx	Xx	Xx	Xx	Xx	Xx
LUTS drugs before study period start	N/A	N/A	N/A	Xx	Xx	Xx
Sum Excluded	Xx	Xx	Xx	Xx	Xx	Xx
Number of patients in the HF cohort, secondary objective 6.	Xx	Xx	Xx	Xx	Xx	Xx

*). Exclusion of patients with multiple desmopressin drugs dispensed on the index date. SOURCE DOCUMENT: SUMTAB.SAS GENERATED: 22:53:48 16JAN2021 DB version DEV: Simulated data, USERID: [name]

Figure 4. Cohort selection flowchart for exploratory analysis, optional figure.

[figure not shown]

Figure 5. Cohort selection flowchart for main analysis, optional figure.

[figure not shown]

Table 9. Primary objective. Incidence of symptomatic hyponatraemia in *country*.

	All Nocdurna ® patients	Nocdurna ®, Male	Nocdurna ®, Female	All LUTS patients	LUTS, Male	LUTS, Female
Variable, time period and population						
All patients - All exposure time						
Number of subjects	3512	2289	1223	1488	931	557
Number of events	493	367	126	129	93	36
Total person years (y)	510.4	335.7	174.7	219.5	138.4	81.0
Mean unadjusted rate of events (events/1000 person-years)	1201.8	1364.8	896.9	759.7	866.9	580.5
Number of patients with more than 1 event	29	25	4	8	5	3
Number of events in patients with more than 1 event	60	52	8	16	10	6
Number of patients with at least one event	Xx	Xx	Xx	Xx	Xx	Xx

[figure not shown]
Desmopressin
One oral lyophilisate per day
Statistical Analysis Plan

Incidence rate (95 % CI)	861.40 (798.94 - 928.74)	1073.58 (989.55 - 1164.75)	688.70 (608.23 - 779.81)	532.61 (466.19 - 608.49)	662.92 (565.25 - 777.46)	427.68 (341.35 - 535.85)
Standard Error of Mean	33.08	44.64	43.66	36.19	53.91	49.20
Scale - one value for each model	0.7468	0.7796	0.6830			
Events first month after						
Index date						
Number of subjects	3512	2289	1223	1488	931	557
Number of events	129	98	31	28	18	10
Total person years (y)	491.4	321.7	169.6	214.7	134.5	80.2
Mean unadjusted rate of events (events/1000	312.8	362.0	220.8	161.9	176.6	137.3
person-years) Variance of unadjusted	642.4	645.5	636.7	661.6	683.9	625.5
rate	042.4	045.5	030.7	001.0	085.9	025.5
Number of patients with				1	1	
more than 1 event	•	•	•	-	-	•
Number of events in				2	2	
patients with more than 1 event						
Number of patients with at	Xx	Xx	Xx	Xx	Xx	Xx
least one event						
Incidence rate (95 % CI)	221.51 (201.40 - 243.62)	285.44 (257.50 - 316.41)	163.73 (139.55 - 192.11)	112.50 (94.11 - 134.48)	126.37 (100.58 - 158.78)	114.02 (87.49 - 148.60)
Standard Error of Mean	10.75	15.00	13.35	10.24	14.72	15.41
Scale - one value for each	0.4641	0.4882	0.4168			
model						
Events after first month						
and onwards						
Number of subjects	2324	1536	788	1017	639	378
Number of events	229	169	60	58	44	14
Total person years (y)	406.1 650.5	268.8	137.3 513.7	179.2 366.3	113.6 415.8	65.6 282.7
Mean unadjusted rate of events (events/1000	030.3	720.6	515.7	300.3	413.8	282.7
person-years)						
Variance of unadjusted rate	611.2	610.4	613.6	603.0	619.4	575.3
Number of patients with	13	11	2	4	3	1
more than 1 event						
Number of events in	26	22	4	8	6	2
patients with more than 1						
event	V	V	V	V	V	V
Number of patients with at least one event		Xx	Xx	Xx	Xx	Xx
Incidence rate (95 % CI)	513.14 (465.63 - 565.51)	628.77 (565.80 - 698.74)	421.10 (359.52 - 493.23)	297.85 (249.79 - 355.15)	386.66 (314.79 - 474.93)	207.78 (151.08 - 285.75)
Standard Error of Mean	25.44	33.85	33.97	26.74	40.57	33.78
Scale - one value for each model	0.6639	0.6936	0.6043			
Patients >= 65 years						
Number of subjects	2435	1573	862	1038	650	388
Number of events	379	281	98	100	69	31
Total person years (y)	352.4	230.4	122.0	152.6	96.6	56.0

Desmopressin Trial Code: One oral lyophilisate per day Statistical Analysis Plan			al Code: 000248 18 Augus E-Statistical Analysis Plan-2509 Page 52			
Mean unadjusted rate of events (events/1000 person-years)	1332	1519	993	843	915	722
Variance of unadjusted	648	646	649	646	661	620
rate Number of patients with more than 1 event	22	19	3	7	4	3
Number of events in patients with more than 1 event	46	40	6	14	8	6
Number of patients with at least one event	Xx	Xx	Xx	Xx	Xx	Xx
Incidence rate (95 % CI)	994.08 (912.02 - 1083.53)	1225.03 (1115.13 - 1345.76)	801.29 (695.41 - 923.29)	616.35 (527.97 - 719.52)	725.40 (600.62 - 876.09)	555.75 (432.23 - 714.58)
Standard Error of Mean Scale - one value for each model	43.70 0.7701	58.75 0.7995	57.94 0.7140	48.67	69.86	71.28

SOURCE DOCUMENT: TABLE1.SAS GENERATED: 22:53:48 16JAN2021 DB version DEV: Simulated data, USERID: [name]

Figure 6. Primary objective. A Cox regression showing time to first event symptomatic hyponatraemia event stratified by patient group and age class in *country*. Survival function for different age grous Nocdurna

Footnote: The figure should have 8 lines, one for each age group (3) and treatment (2). SOURCE DOCUMENT: COX1.SAS GENERATED: 22:53:48 16JAN2021 DB version DEV: Simulated data, USERID: [name]

Table 10	Secondary ob	iective 1 Der	nooranhic and	health char	racteristics in	country
1 abic 10.	Secondary 00		nographic and	incartin cha	lacteristics in	1 country.

	All Nocdurna ® patients	Nocdurna ®, Male	Nocdurna ®, Female	All LUTS patients	LUTS, Male	LUTS, Female
Age (year)						
Ν	230	100	230	100	230	100
Mean (SD)	61.17 (8.36)	62.81 (9.00)	61.17 (8.36)	62.81 (9.00)	61.17 (8.36)	62.81 (9.00)
Median	62.05	63.13	62.05	63.13	62.05	63.13
Range	44.7 , 82.3	40.0 , 85.0	44.7 , 82.3	40.0 , 85.0	44.7 , 82.3	40.0,85.0
IQR	56.0 , 74.0	55.0,75.0	56.0 , 74.0	55.0,75.0	56.0 , 74.0	55.0,75.0
Missing values	0	0	0	0	0	0
Repeat above 7 limes for						
Number of hospitalisations						
Number of emergency room visits						
Exposure time						

Ferring Pharmaceuticals

ender, n and (%)						
Male	99 (43)	99 (43)	N/A	49 (49)	49 (49)	N/A
Female	131 (57)	N/A	131 (57)	51 (51)	N/A	51 (51)
epeat the above 3 lines or						
olyuria R35, please heck national nplementation of R35	Xx (xx)	Xx (xx)	Xx (xx)	Xx (xx)	Xx (xx)	Xx (xx)
olyuria R35.9A	Xx (xx)	Xx (xx)	Xx (xx)	Xx (xx)	Xx (xx)	Xx (xx)
lykturi R35.9B	Xx (xx)	Xx (xx)	Xx (xx)	Xx (xx)	Xx (xx)	Xx (xx)
ollakisuri R35.9C	Xx (xx)	Xx (xx)	Xx (xx)	Xx (xx)	Xx (xx)	Xx (xx)
biabetes mellitus; E10, 11, E12, E13 and E14	Xx (xx)	Xx (xx)	Xx (xx)	Xx (xx)	Xx (xx)	Xx (xx)
viabetes insipidus, E23.2	Xx (xx)	Xx (xx)	Xx (xx)	Xx (xx)	Xx (xx)	Xx (xx)
overactive bladder, N31.0, 131.2, N31.9, N39.4, 39.1 and ATC G04BD	Xx (xx)	Xx (xx)	Xx (xx)	Xx (xx)	Xx (xx)	Xx (xx)
enign prostatic yperplasia, N40, D29.1 nd ATC G04C	Xx (xx)	Xx (xx)	Xx (xx)	Xx (xx)	Xx (xx)	Xx (xx)
rinary tract infection, 39.0, N30, N10	Xx (xx)	Xx (xx)	Xx (xx)	Xx (xx)	Xx (xx)	Xx (xx)
olydipsia, R36.1	Xx (xx)	Xx (xx)	Xx (xx)	Xx (xx)	Xx (xx)	Xx (xx)
leart failure, 150	Xx (xx)	Xx (xx)	Xx (xx)	Xx (xx)	Xx (xx)	Xx (xx)
lypertension, I10	Xx (xx)	Xx (xx)	Xx (xx)	Xx (xx)	Xx (xx)	Xx (xx)
lyperlipidaemi, E78	Xx (xx)	Xx (xx)	Xx (xx)	Xx (xx)	Xx (xx)	Xx (xx)
trial fibrillation, I48	Xx (xx)	Xx (xx)	Xx (xx)	Xx (xx)	Xx (xx)	Xx (xx)
besity, E66	Xx (xx)	Xx (xx)	Xx (xx)	Xx (xx)	Xx (xx)	Xx (xx)
idney disease, N18, N19	Xx (xx)	Xx (xx)	Xx (xx)	Xx (xx)	Xx (xx)	Xx (xx)
ystic fibrosis, E84	Xx (xx)	Xx (xx)	Xx (xx)	Xx (xx)	Xx (xx)	Xx (xx)
re-eclampsia, O11, O14	Xx (xx)	Xx (xx)	Xx (xx)	Xx (xx)	Xx (xx)	Xx (xx)
hronic lung disease, J40- 47, J60-J70, J80, J82, J84, 95-J99	Xx (xx)	Xx (xx)	Xx (xx)	Xx (xx)	Xx (xx)	Xx (xx)
iver disease, K70-K77, 10 and ATC N07BB	Xx (xx)	Xx (xx)	Xx (xx)	Xx (xx)	Xx (xx)	Xx (xx)
ancer, C00-C43, C45- 97	Xx (xx)	Xx (xx)	Xx (xx)	Xx (xx)	Xx (xx)	Xx (xx)
rostate cancer, C61	Xx (xx)	Xx (xx)	Xx (xx)	Xx (xx)	Xx (xx)	Xx (xx)
ladder cancer, C67	Xx (xx)	Xx (xx)	Xx (xx)	Xx (xx)	Xx (xx)	Xx (xx)

Desmopressin One oral lyophilis Statistical Analys			Trial Code: 00024	48	E-Statistical Analy	18 August 2021 sis Plan-25098 (1.0) Page 55 of 91
Dementia F00, F01, F02, F03, F04, G30, G31.0, G31.1	Xx (xx)	Xx (xx)	Xx (xx)	Xx (xx)	Xx (xx)	Xx (xx)
Co-medication	Xx (xx)	Xx (xx)	Xx (xx)	Xx (xx)	Xx (xx)	Xx (xx)
Loperamide, A07DA03	Xx (xx)	Xx (xx)	Xx (xx)	Xx (xx)	Xx (xx)	Xx (xx)
Antidiabetics, A10	Xx (xx)	Xx (xx)	Xx (xx)	Xx (xx)	Xx (xx)	Xx (xx)
Sulfonylureas including chlorpropamide, A10BB	Xx (xx)	Xx (xx)	Xx (xx)	Xx (xx)	Xx (xx)	Xx (xx)
Amiodarone, C01BD01	Xx (xx)	Xx (xx)	Xx (xx)	Xx (xx)	Xx (xx)	Xx (xx)
Antihypertensive, C02	Xx (xx)	Xx (xx)	Xx (xx)	Xx (xx)	Xx (xx)	Xx (xx)
Diuretics, C03	Xx (xx)	Xx (xx)	Xx (xx)	Xx (xx)	Xx (xx)	Xx (xx)
Special diuretics, C03A, C03B, C03C, C03D and C03E	Xx (xx)	Xx (xx)	Xx (xx)	Xx (xx)	Xx (xx)	Xx (xx)
Beta blocking agents, C07	Xx (xx)	Xx (xx)	Xx (xx)	Xx (xx)	Xx (xx)	Xx (xx)
Special beta blocking agents, C07B, C07C and C07D	Xx (xx)	Xx (xx)	Xx (xx)	Xx (xx)	Xx (xx)	Xx (xx)
Calcium channel blockers and diuretics, C08G	Xx (xx)	Xx (xx)	Xx (xx)	Xx (xx)	Xx (xx)	Xx (xx)
ACE inhibitors, C09A	Xx (xx)	Xx (xx)	Xx (xx)	Xx (xx)	Xx (xx)	Xx (xx)
Special ACE inhibitors, C09BA	Xx (xx)	Xx (xx)	Xx (xx)	Xx (xx)	Xx (xx)	Xx (xx)
Angiotensin II receptor blockers, C09C	Xx (xx)	Xx (xx)	Xx (xx)	Xx (xx)	Xx (xx)	Xx (xx)
Angiotensin II receptor blockers (combinations), C09D	Xx (xx)	Xx (xx)	Xx (xx)	Xx (xx)	Xx (xx)	Xx (xx)
Lipid-modifying agents, C10	Xx (xx)	Xx (xx)	Xx (xx)	Xx (xx)	Xx (xx)	Xx (xx)
Vasopressin and analogues (incl. desmopressin), H01BA	Xx (xx)	Xx (xx)	Xx (xx)	Xx (xx)	Xx (xx)	Xx (xx)
Systemic corticosteroids, H02	Xx (xx)	Xx (xx)	Xx (xx)	Xx (xx)	Xx (xx)	Xx (xx)
Antiepileptic, N03A	Xx (xx)	Xx (xx)	Xx (xx)	Xx (xx)	Xx (xx)	Xx (xx)
Carbamazepine and lamotrigine, N03AF01 and N03AX09	Xx (xx)	Xx (xx)	Xx (xx)	Xx (xx)	Xx (xx)	Xx (xx)
Non-selective monoamine reuptake inhibitors, N06AA	Xx (xx)	Xx (xx)	Xx (xx)	Xx (xx)	Xx (xx)	Xx (xx)
Selective serotonin reuptake inhibitors, N06AB	Xx (xx)	Xx (xx)	Xx (xx)	Xx (xx)	Xx (xx)	Xx (xx)

Desmopressin One oral lyophilis Statistical Analys	• •		Trial Code: 0002	248	18 August 2021 E-Statistical Analysis Plan-25098 (1.0) Page 56 of 91		
Chlorpromazine, N05AA01	Xx (xx)	Xx (xx)	Xx (xx)	Xx (xx)	Xx (xx)	Xx (xx)	
NSAIDs, M01A	Xx (xx)	Xx (xx)	Xx (xx)	Xx (xx)	Xx (xx)	Xx (xx)	
Opioids, N02A	Xx (xx)	Xx (xx)	Xx (xx)	Xx (xx)	Xx (xx)	Xx (xx)	
Phenothiazines with aliphatic side-chain, N05AA	Xx (xx)	Xx (xx)	Xx (xx)	Xx (xx)	Xx (xx)	Xx (xx)	
Chlorpromazine, N05AA01	Xx (xx)	Xx (xx)	Xx (xx)	Xx (xx)	Xx (xx)	Xx (xx)	
Lithium, N05AN01	Xx (xx)	Xx (xx)	Xx (xx)	Xx (xx)	Xx (xx)	Xx (xx)	
Antidepressants, N06A	Xx (xx)	Xx (xx)	Xx (xx)	Xx (xx)	Xx (xx)	Xx (xx)	
Anti-inflammatory agents, non-steroids , M01A	Xx (xx)	Xx (xx)	Xx (xx)	Xx (xx)	Xx (xx)	Xx (xx)	
Overactive bladder, G04BD	Xx (xx)	Xx (xx)	Xx (xx)	Xx (xx)	Xx (xx)	Xx (xx)	
Benign prostatic hyperplasia, G04C	Xx (xx)	Xx (xx)	Xx (xx)	Xx (xx)	Xx (xx)	Xx (xx)	
Desmopressin, H01BA02	Xx (xx)	Xx (xx)	Xx (xx)	Xx (xx)	Xx (xx)	Xx (xx)	
Patients >= 65 years	Xx (xx)	Xx (xx)	Xx (xx)	Xx (xx)	Xx (xx)	Xx (xx)	
Repeat all the above rows for this population	Xx (xx)	Xx (xx)	Xx (xx)	Xx (xx)	Xx (xx)	Xx (xx)	

SOURCE DOCUMENT: DEMOGRAPHY_SWEDEN.SAS GENERATED: 22:53:48 16SEP2013 DB version DEV: ART_03, USER_ID [name]. Calculated on the index date, except for exposure time as defined in this SAP.

	Nocdurna ® patients								
	Wit	hout contraindic	ations	N.	With contraindicat	ions			
	Both gender	Male	Female	Both gender	Male	Female			
Age (year)									
Ν	230	100	230	100	230	100			
Mean (SD)	61.17 (8.36)	62.81 (9.00)	61.17 (8.36)	62.81 (9.00)	61.17 (8.36)	62.81 (9.00)			
Median	62.05	63.13	62.05	63.13	62.05	63.13			
Range	44.7 , 82.3	40.0,85.0	44.7 , 82.3	40.0 , 85.0	44.7 , 82.3	40.0 , 85.0			
IQR	56.0,74.0	55.0,75.0	56.0 , 74.0	55.0,75.0	56.0 , 74.0	55.0,75.0			
Missing values	0	0	0	0	0	0			

Table 11. Secondary objective 1. Demographic and health characteristics in *country* divided according to contraindications.

Repeat the structure from the previous table (a long

table!)

SOURCE DOCUMENT: DEMOcontra_SWEDEN.SAS GENERATED: 22:53:48 16FEB2021 DB version DEV: ART_03, USER_ID [name]. Calculated on the index date, except for exposure time as defined in this SAP. Only patients from 4 out of 5 Danish regions reporting to the National Lab database.

Table 12. Secondary objective 1. Demographic and health characteristics in *Denmark* stratified according to patients with sodium measurements and patients without sodium measurements.

Repeat table shell from Table 10 and stratify according to patient with and without measurements.

Figures of continuous variables.

Figure 7. Secondary objective 1. A Boxplot of age divided by treatment group in *country*.

[figure not shown]

Figure 8. Secondary objective 1. A symmetry plot of age divided by treatment group in country (only one group is shown).

[figure not shown]

Figure 9. Secondary objective 1. A normal quantile plots of age divided by treatment group (Nocdurna ® and LUTS) in *country* (only one group is shown).

[figure not shown]

Figure 10. Secondary objective 1. A normal probability plots of age divided by treatment group in *country* (only one group is shown).

[figure not shown]

Figure 11. Secondary objective 1. A Boxplot of exposure time divided by treatment group in *country*.

Repeat Figure 7 with exposure time instead of age.

Figure 12. Secondary objective 1. A symmetry plot of exposure time divided by treatment group in country.

Repeat Figure 8 with exposure time instead of age.

Figure 13. Secondary objective 1. A normal quantile plots of exposure time divided by treatment group (Nocdurna ® and LUTS) in *country*.

Repeat Figure 9 with exposure time instead of age.

Figure 14. Secondary objective 1. A normal probability plots of exposure time divided by treatment group in *country*.

Repeat Figure 10 with exposure time instead of age.

Table 13. Secondary objective 2. Incidence of hyponatraemia requiring hospital intensive care (ICU) in *Sweden*.

Repeat Table 9 with changed outcome

Figure 15. Secondary objective 2. A Cox regression showing time to first event hyponatraemia requiring hospital intensive care (ICU) stratified by patient group and age class in Sweden.

Table 14. Secondary objective 3. Incidence of clinically significant hyponatraemia (lab value) in *Denmark*: serum sodium concentration <130 mmol/L

Repeat Table 9 with changed outcome

